8.2.4.1.2 Serious Adverse Events

The investigator is responsible for ensuring that all serious adverse events observed by the investigator or reported by the subject that occur after signing of the informed consent through end of study are reported using the Event CRF.

All serious adverse events will be collected, recorded and reported to the sponsor or designee within 24 hours of the investigator's knowledge of the event, as indicated in Section 11.4. The investigator will submit any updated serious adverse event data to the sponsor within 24 hours of it being available.

The criteria for grade 4 in the CTCAE grading scale differs from the regulatory criteria for serious adverse events. The investigator is to determine whether these grade 4 abnormalities are serious adverse events based on the definition of serious adverse events as per Appendix 4 (Section 11.4).

8.2.4.1.3 Serious Adverse Events After the Protocol-required Reporting Period

After End of Study, there is no requirement to actively monitor study subjects after the study has ended with regards to study subjects treated by the investigator. However, if the investigator becomes aware of serious adverse events suspected to be related to investigational product, then these serious adverse events will be reported to Amgen within 24 hours following the investigator's awareness of the event.

Serious adverse events reported outside of the protocol-required reporting period will be captured within the safety database as clinical trial cases and handled accordingly based on relationship to investigational product. If further safety related data is needed to fulfill any regulatory reporting requirements for a reportable event, then additional information may need to be collected from the subject's records after the subject ends the study.

The method of recording, evaluating, and assessing causality of adverse events, adverse device effects, and serious adverse events and the procedures for completing and transmitting serious adverse event reports are provided in Section 11.4.

8.2.4.2 Method of Detecting Adverse Events and Serious Adverse Events

Care will be taken not to introduce bias when detecting adverse events and/or serious adverse events. Open-ended and non-leading verbal questioning of the subject is the preferred method to inquire about adverse event occurrence.

8.2.4.3 Follow-up of Adverse Events and Serious Adverse Events

After the initial adverse event/serious adverse event report, the investigator is required to proactively follow each subject at subsequent visits/contacts. All adverse events and serious adverse events will be followed until resolution, stabilization, until the event is otherwise explained, or the subject is lost to follow-up (as defined in Section 7.3). Further information on follow-up procedures is given in Section 11.4.

All new information for previously reported serious adverse events must be sent to Amgen within 24 hours following knowledge of the new information. If specifically requested, the investigator may need to provide additional follow-up information, such as discharge summaries, medical records, or extracts from the medical records. Information provided about the serious adverse event must be consistent with that recorded on the Event CRF.

8.2.4.4 Regulatory Reporting Requirements for Serious Adverse Events

If subject is permanently withdrawn from protocol-required therapies because of a serious adverse event, this information must be submitted to Amgen.

Prompt notification by the investigator to the sponsor of serious adverse events is essential so that legal obligations and ethical responsibilities towards the safety of subjects and the safety of a study treatment under clinical investigation are met.

The sponsor has a legal responsibility to notify both the local regulatory authority and other regulatory agencies about the safety of a study treatment under clinical

investigation. The sponsor will comply with country-specific regulatory requirements relating to safety reporting to the regulatory authority, IRBs/IECs, and investigators.

Individual safety reports must be prepared for suspected unexpected serious adverse reactions according to local regulatory requirements and sponsor policy and forwarded to investigators as necessary.

An investigator who receives an individual safety report describing a serious adverse event or other specific safety information (eg, summary or listing of serious adverse events) from the sponsor will file it along with the Investigator's Brochure and will notify the IRB/IEC, if appropriate according to local requirements.

To comply with worldwide reporting regulations for serious adverse events, the treatment assignment of subjects who develop serious, unexpected, and related adverse events may be unblinded by Amgen before submission to regulatory authorities. Aggregate analyses may also be unblinded by the Safety Assessment Team, as appropriate. Investigators will receive notification of related serious adverse events reports sent to regulatory authorities in accordance with local requirements.

8.2.4.5 Safety Monitoring Plan

Subject safety will be routinely monitored as defined in Amgen's safety surveillance and signal management processes.

8.2.4.6 Pregnancy and Lactation

Details of all pregnancies and/or lactation in female subjects and female partners of male subjects will be collected after the start of study treatment and until 16 weeks after the last dose of investigational product.

If a pregnancy is reported, the investigator is to inform Amgen within 24 hours of learning of the pregnancy and/or lactation and is to follow the procedures outlined in Section 11.5. Amgen Global Patient Safety will follow-up with the investigator regarding additional information that may be requested.

Abnormal pregnancy outcomes (eg, spontaneous abortion, fetal death, stillbirth, congenital anomalies, and ectopic pregnancy) are considered serious adverse events.

Further details regarding pregnancy and lactation are provided in Section 11.5.

8.2.4.7 Adverse Device Effects

In order to fulfill regulatory reporting obligations worldwide, the investigator is responsible for the detection and documentation of any adverse device effects that occur during the study with such devices.

An adverse device effect is any adverse event related to the use of a combination product or medical device. Adverse device effects include adverse events resulting from insufficient or inadequate instructions for use, adverse events resulting from any malfunction of the device, or adverse events resulting from use error or from intentional misuse of the device.

All adverse device effects are to be reported as adverse events following the same reporting periods and procedures.

Product complaints are described in Section 6.1.5.

Further details regarding adverse device effects can be found in Section 11.4.

8.2.5 Clinical Laboratory Assessments

Refer to Section 11.2 for the list of clinical laboratory tests to be performed and to the Schedule of Activities (Table 1-1) for the timing and frequency.

The investigator is responsible for reviewing laboratory test results and recording any clinically relevant changes occurring during the study in the Event CRF.

All protocol-required laboratory assessments, as defined in Section 11.2, must be conducted in accordance with the laboratory manual and the Schedule of Activities (Table 1-1).

Pregnancy Testing

A urine pregnancy test should be completed for females of childbearing potential as per the Schedule of Activities (Table 1-1).

Note: Females who have undergone a bilateral tubal ligation/occlusion should have pregnancy testing per protocol requirements. (If a female subject, or the partner of a male subject, becomes pregnant it must be reported on the Pregnancy Notification Form, see Figure 11-3). Refer to Section 11.5 for contraceptive requirements.

Additional on-treatment pregnancy testing may be performed at the investigator's discretion or as required per local laws and regulations.

8.2.6 Pharmacogenetic Assessments

If the subject consents to the optional pharmacogenetic portion of this study, DNA analyses may be performed. These optional pharmacogenetic analyses focus on inherited genetic variations to evaluate their possible correlation to the disease and/or responsiveness to the therapies used in this study. The goals of the optional studies include the use of genetic markers to help in the investigation of migraines and/or to identify subjects who may have positive or negative response to erenumab. No additional samples are collected for this part of the study. For subjects who consent to this/these analysis/analyses, DNA may be extracted from the cell pellet collected in the plasma tube used for the biomarker development sample.

The final disposition of samples is described in Section 11.6.

8.2.7 Biomarkers

Biomarkers are objectively measured and evaluated indicators of normal biologic processes, pathogenic processes, or pharmacologic responses to a therapeutic intervention.

8.2.7.1 Biomarker Development/Future Research

Biomarker Development refers to using samples collected for Biomarker Discovery for future research after the study ends.

Biomarker development can be useful in developing markers to identify disease subtypes, guide therapy, and/or predict disease severity.

If consent is provided by subjects, biomarker discovery samples collected at the time points specified in the Schedule of Activities will be retained for future biomarker development as described in Appendix 6 (Section 11.6).

Amgen or another third-party manufacturer may attempt to develop test(s) designed to identify subjects most likely to respond positively or negatively to erenumab to investigate and further understand migraines.

9. Statistical Considerations

9.1 Statistical Hypotheses

The primary hypothesis is that preventive treatment with monthly administration of erenumab is superior to placebo in reducing duration of moderate or severe headache pain in subjects with HFEM who have previously failed at least 1 migraine preventive treatment.

9.2 Sample Size Determination

A total sample size of 576 subjects (288 subjects per group including 10% dropouts) provides at least a 90% power for the primary efficacy hypothesis. The statistical power for secondary efficacy hypotheses ranges from 81% to > 99% (Table 9-1).

Table 9-1. Sample Size Assumptions and Statistical Powers for Primary andSecondary Efficacy Endpoints for a Total Sample Size of 576 Subjects Including a10% Attrition Rate due to Dropout

Hypothesis	Assumed Treatment Effect (Common SD)	Power
Primary:	- 16.7 (50)	96%
Change from baseline in mean monthly hours of at least moderate headache pain intensity over months 1, 2, and 3		
Secondary: Change from baseline in mean monthly		
MFIQ physical function domain score over months 1, 2, and 3	-9.2 (18.0)	> 99%
MFIQ usual activities domain score over months 1, 2, and 3	-7.5 (19)	> 99%
MFIQ emotional function domain score over months 1, 2, and 3	-11.5 (22)	> 99%
MFIQ social function domain score over months 1, 2, and 3	-6.9 (20)	97%
Average duration of at least moderate migraine pain intensity in migraine attacks occurring over months 1, 2, and 3 ^a	-2.0 (8)	81%
Average peak migraine pain intensity over months 1, 2, and 3	-0.11 (0.44)	81%

MFIQ = Migraine Functional Impact Questionnaire.

Note: All power calculations are based on a 2-sided significance level of 0.05. The assumed treatment effects and common standard deviations are derived or chosen from a subset of placebo-treated and erenumab-140 mg-treated subjects in erenumab Study 20120296 with high-frequency episodic migraine (ie, 7 to 14 monthly migraine days) and having at least 4 moderate-to-severe migraine attacks at baseline. ^a If a subject did not have any migraine attacks in a given month, the duration of at least moderate migraine pain intensity was counted as 0.

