6.4 Measures to Minimize Bias: Randomization and Blinding

6.4.1 Method of Treatment Assignment

Subjects will be randomized in a 1:1 allocation ratio to either erenumab or placebo in a double-blind manner after meeting all the post-baseline randomization requirements described in Section 5.5.

The randomization number will be assigned by the IRT. The randomization number is different than the subject identification number and will not be used by the site as a subject identifier.

The randomization date is to be documented in the subject's medical record and on the enrollment CRF.

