9.4.2 Methods of Analyses

9.4.2.1 General Considerations

Summary statistics will be computed by treatment group and visit. For continuous endpoints, the following descriptive statistics will be computed: number of observations, means, medians, standard deviations, standard errors, first and third quartiles, minimums and maximums, and 2-sided 95% CIs of the means (CIs will be provided for efficacy endpoints only). For categorical endpoints, the summaries will contain the number and percentage of subjects in each category.

The primary analysis method utilizing a repeated measures linear mixed effects model will include all observed data regardless of treatment adherence.

A sequential testing procedure will be used to maintain the family-wise type 1 error $\alpha = 0.05$ between the primary and secondary endpoints following the prespecified order below. An endpoint will only be tested for statistical significance if the endpoint tested in the previous step is statistically significant at 2-sided significance level of 0.05.

1. Primary endpoint: change from baseline in mean monthly hours of at least moderate headache pain intensity over months 1, 2, and 3

- 2. Secondary endpoints: change from baseline in mean monthly function domain score over months 1, 2, and 3, as measured by the MFIQ using the Hochberg procedure
 - Impact on physical functioning
 - Impact on usual activities
 - Impact on emotional functioning
 - Impact on social functioning
- Secondary endpoint: change from baseline in mean monthly average duration of at least moderate pain intensity in migraine attacks occuring over months 1, 2, and 3 (migraine attacks as defined in Section 11.1)
- 4. Secondary endpoint: change from baseline in mean monthly average peak migraine pain intensity over months 1, 2, and 3, as assessed by the 11-point NRS

Endpoint	Statistical Analysis Methods
Primary	The primary endpoint will be analyzed using a linear mixed effects model including treatment group, baseline value, scheduled visit, and the interaction of treatment group with scheduled visit, without any imputation for missing data.
Secondary	The secondary endpoints will be analyzed using a linear mixed effects model including treatment group, baseline value, scheduled visit, and the interaction of treatment group with scheduled visit, without any imputation for missing data.
Exploratory	Detailed primary analysis method for exploratory endpoints will be described in the SAP.

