3.2 Sample Size

A total sample size of 576 subjects (288 subjects per group including 10% dropouts) provides at least a 90% power for the primary efficacy hypothesis. The statistical power for secondary efficacy hypotheses ranges from 81% to > 99% (Table 3-1).

Table 3-1. Sample Size Assumptions and Statistical Powers for Primary and
Secondary Efficacy Endpoints for a Total Sample Size of 576 Subjects
Including a 10% Attrition Rate due to Dropout

Hypothesis	Assumed Treatment Effect	Power
------------	--------------------------------	-------

	(Common SD)	
Primary:	-16.7 (50)	96%
Change from baseline in mean monthly hours of at least moderate headache pain intensity over months 1, 2, and 3		
Secondary: Change from baseline in mean monthly		
MFIQ physical function domain score over months 1, 2, and 3	-9.2 (18.0)	> 99%
MFIQ usual activities domain score over months 1, 2, and 3	-7.5 (19)	> 99%
MFIQ emotional function domain score over months 1, 2, and 3	-11.5 (22)	> 99%
MFIQ social function domain score over months 1, 2, and 3	-6.9 (20)	97%
Average duration of at least moderate migraine pain intensity in migraine attacks occurring over months 1, 2, and 3 ^a	-2.0 (8)	81%
Average peak migraine pain intensity over months 1, 2, and 3	-0.11 (0.44)	81%

MFIQ = Migraine Functional Impact Questionnaire

Note: All power calculations are based on a 2-sided significance level of 0.05. The assumed treatment effects and common standard deviations are derived or chosen from a subset of placebo-treated and erenumab-140mg-treated subjects in erenumab Study 20120296 with high-frequency episodic migraine (ie, 7 to 14 monthly migraine days) and having at least 4 moderate-to-severe migraine attacks at baseline. ^a If a subject did not have any migraine attacks in a given month, the duration of at least moderate migraine pain intensity **was counted as 0**.

4. Covariates and Subgroups

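### The power tables give stand-alone power for hypotheses tested in a fixed sequence; the stated 81% for peak pain, tested last, would need almost perfect correlation with attack duration

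*Protocol*

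**What the plan says.** Protocol 9.2 plans 576 subjects, 288 in each arm with an allowance of 10% for dropout, and claims 90% power or more for the primary. On the other endpoints it reads: "The statistical power for secondary efficacy hypotheses ranges from 81% to > 99" percent. SAP 3.2 makes the same claim for its own table.

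Protocol Table 9-1 and SAP Table 3-1 each list one effect, one common SD and one power per endpoint. Attack duration and peak pain are both given 81%. The table note gives one significance level: "All power calculations are based on a 2-sided significance level of 0.05".

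The testing rule is in Protocol 9.4.2.1, and also in the synopsis and SAP 9.1: "An endpoint will only be tested for statistical significance if the endpoint tested in the previous step is statistically significant". The order is:

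1. the primary endpoint;
2. the four MFIQ domains, "over months 1, 2, and 3, as measured by the MFIQ using the Hochberg procedure";
3. average duration of at least moderate pain in migraine attacks;
4. peak pain: "4. Secondary endpoint: change from baseline in mean monthly average peak migraine pain intensity over months 1, 2, and 3".

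Neither document says that the tabulated powers disregard this order, gives a correlation between endpoints, or says how many MFIQ domains must be significant before step 3 is tested.

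**The concern.** A reader will take the power for a secondary hypothesis as the chance that the planned procedure declares it significant, if the assumed effects are true. In a fixed sequence that chance depends on every earlier step. Steps 1 and 2 have high power and cost little. Step 3 has only 81% power of its own, and step 4 can be reached only through it. Listing 81% for step 4 as well therefore treats the step 3 gate as free.

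What is at stake is the stated chance of a confirmatory claim on peak pain. If it is nearer 70% than 81%, the sponsor should know that when ranking the endpoints and when interpreting a failure at step 3 or 4.

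**Working it through.** **Inputs** (Protocol 9.2 and Table 9-1; the same values are in SAP Table 3-1). There are 288 subjects per arm with 10% dropout, so 288 × 0.9 ≈ 259 evaluable per arm. Allocation is 1:1 (Protocol 6.4.1) and alpha is two-sided 0.05. No correlation is given, so a range is assumed.

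**Step 1: reproduce the plan's figures.** Power of one test ≈ Φ(d × √(n/2) − 1.96), where d = effect/SD and √(259/2) = 11.38.

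| Endpoint | d | d × 11.38 | Power alone | Stated |
|---|---|---|---|---|
| Primary | 16.7/50 = 0.334 | 3.80 | 96.7% | 96% |
| MFIQ physical | 9.2/18 = 0.511 | 5.82 | 99.99% | > 99% |
| MFIQ usual activities | 7.5/19 = 0.395 | 4.49 | 99.4% | > 99% |
| MFIQ emotional | 11.5/22 = 0.523 | 5.95 | > 99.9% | > 99% |
| MFIQ social | 6.9/20 = 0.345 | 3.93 | 97.5% | 97% |
| Attack duration | 2.0/8 = 0.25 | 2.84 | 81.2% | 81% |
| Peak pain | 0.11/0.44 = 0.25 | 2.84 | 81.2% | 81% |

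Every row agrees to within a point, so the tables hold stand-alone powers. The noncentral t gives 81.05% for the last two rows.

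**Step 2: bound for peak pain from the last two steps only.** Power for peak pain ≤ P(duration significant and peak pain significant). With independent tests this is 0.8119² = 65.9%. For other correlations it is a bivariate normal probability with both means at 2.84 and both cut-offs at 1.96. The bound holds whatever rule applies at the MFIQ step. It reaches 80.0% at a correlation of 0.994 and 80.5% at 0.998.

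**Step 3: the full sequence.** Seven normal test statistics with the means in the table share one assumed correlation, and Hochberg is applied to the four MFIQ domains (4,000,000 draws; exact products at correlation 0).

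| Correlation | Pair bound, peak pain | Peak pain, all four domains required | Peak pain, one domain enough | Duration, all four domains required |
|---|---|---|---|---|
| 0 | 65.9% | 61.8% | 63.8% | 76.2% |
| 0.5 | 70.4% | 69.2% | 69.7% | 79.0% |
| 0.7 | 72.8% | 72.4% | 72.6% | 80.2% |
| 0.9 | 76.4% | 76.4% | 76.4% | 81.1% |
| 0.99 | 79.7% | 79.7% | 79.7% | 81.2% |

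With unequal correlations (0.8 among MFIQ domains, 0.6 among diary endpoints, 0.4 across, all four domains required), power is 79.1% for duration and 70.3% for peak pain.

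MFIQ social functioning after the primary is 0.9672 × 0.9754 = 94.3% at correlation 0 and 95.9% at 0.9.

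**Step 4: does the step 3 opening rule matter?** Suppose the primary and one MFIQ domain are strongly effective and the other five endpoints are null. If one significant domain opens step 3, the null domains and the duration test can each produce a false positive at close to 5%. With independence that is roughly 1 − 0.95 × 0.95 ≈ 9.75%. The computed family-wise error is 9.7%, 8.5% and 5.9% at correlations 0, 0.5 and 0.9. If all four domains are required it is 4.9%, 4.6% and 3.5%.

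**The case against.** The strongest reply is that nothing is miscalculated and only a label is missing. The tables show one effect, one SD and one power per row, with no correlation, and use the same 0.05 level even for the MFIQ rows that go through Hochberg. A statistician can infer that these are per-endpoint powers, and quoting such powers is common. The protocol sets a power target only for the primary, so no sample-size decision rests on the 81%. Once data exist, no test or estimate changes. These points stand and limit the weight of the concern. They do not make 81% the power of peak pain under the planned procedure, and non-statistical readers of the plan will not make the inference.

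A second reply concerns the range. The 62% end needs all seven statistics to be independent. That is unlikely for duration and peak pain, which come from the same diary and are both set to 0 when there is no migraine in the month (for peak pain, no migraine day with a pain score). This is fair, and the low end should be read as a limit. The pair bound needs only the duration–peak correlation, and it still leaves 76.4% at 0.9.

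Third, 0.998 is a rounding threshold, and the shortfall at 0.99 is only about 1.5 points. That is also true. The stated 96% for a computed 96.7% suggests that the tables may truncate. Truncation would make the requirement stricter, because the pair bound is still only 80.7% at a correlation of 0.999.

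Finally, the step 3 rule is a type I error question, and it moves power for peak pain by only 2.0 points at correlation 0 and not at all at 0.9. Other valid gatekeeping procedures exist. The plan specifies none of them, however, and power through the sequence cannot be stated until the rule is fixed.

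**Conclusion.** The concern holds. The tabulated powers are right as stand-alone figures and wrong as the power of hypotheses tested in the planned sequence. The shortfall that matters is peak pain: 81% stated, against about 62% to 76% for a common correlation of 0 to 0.9 when all four MFIQ domains are required (64% to 76% if one is enough). That is roughly 5 to 19 points too high. The exact figure depends on correlations that the documents do not give. The conclusion that 81% is overstated does not, short of near-perfect correlation between duration and peak pain.

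Attack duration loses at most about 5 points, and the MFIQ domains stay at about 94% or more. Primary power, sample size, alpha and the analysis model are unaffected. This should be corrected, but it does not threaten the trial's main conclusion.

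**What to change.** - In Protocol Table 9-1 and SAP Table 3-1, and in the sentence above each, label the present figures as stand-alone power.
- Add a column with power through the sequence, stating the correlations assumed. These are best estimated from the Study 20120296 subset that already supplied the effects and SDs. A small range is acceptable if they cannot be estimated.
- In Protocol 9.4.2.1, the synopsis and SAP 9.1, state that step 3 is tested only when all four MFIQ domains are significant under Hochberg. Of the two natural readings, this is the one that keeps the family-wise error at 0.05.

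The cost is one re-run of the planning calculation, a label and a column in two tables, and one added sentence in each testing section. The secondary power figures will look less favourable. If the sponsor had meant one significant domain to open step 3, the all-four rule is stricter.
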